3.2. Study Endpoints

3.2.1. Safety Endpoints

The primary safety endpoints are clinical laboratory evaluations (hematology, chemistry, urinalysis), physical examination findings, vital sign measurements, safety 12-lead ECG parameters, incidence and severity of AEs, and incidence of SAEs.

3.2.2. Pharmacokinetic Endpoints

The secondary PK samples will be assessed for AV-1 concentrations. The following PK parameters for AV-1 will be calculated as endpoints:

- C_{max}: Maximum observed serum drug concentration
- T_{max}: Time to reach maximum serum concentration following drug administration
- AUC_{0-tlast}: Area under the serum concentration versus time curve from time 0 to the last quantifiable concentration in serum
- AUC₀₋₄₈: Area under the serum concentration versus time curve from time 0 to 48 hours postdose
- AUC_{0-∞}: Extrapolation of the area under the curve from time 0 to infinity
- t_{1/2}: Terminal half-life
- CL: Total serum clearance
- V_z: Volume of distribution during the terminal phase

3.2.3. Immunogenicity Endpoints

Incidence of anti-AV-1 antibodies as measured by the proportion of subjects with detectable anti-AV-1 antibody signal in serum, including treatment-emergent anti-AV-antibodies, using an electrochemiluminescence (ECL) enzyme-linked immunosorbent assay (ELISA).

4. General Statistical Considerations

All data collected will be presented in data listings. Data from subjects excluded from an analysis population will be presented in the data listings but not included in the calculation of summary statistics.

For categorical variables, frequencies and percentages will be presented. Continuous variables will be summarized using descriptive statistics (number of subjects, mean, median, standard deviation [SD], minimum, and maximum).

Unless specified otherwise, baseline will be defined as the last non-missing assessment prior to the study drug administration. Unscheduled visits will be used in determining baseline.

Unless otherwise indicated, outputs which are summarized by treatment will be summarized for each dose level for subjects on active study drug; subjects who receive placebo will be pooled into a single group.

The study day of dosing will be considered as Day 1. Study day will be calculated relative to the first dose date as follows:

- If assessment date is on or after the first dose of study drug administration, then Study Day = Assessment Date - Dose Date + 1
- Otherwise, Study Day = Assessment Date Dose Date

4.1. Sample Size

This study will enroll a total of 40 subjects in 5 cohorts of 8 subjects each and up to 8 subjects for replacements as necessary. Each cohort will consist of 6 AV-1 treated and 2 placebo treated subjects. The sample size (N = 40) for this study is based on clinical and practical considerations and not on a formal statistical power calculation. The sample size is considered sufficient to evaluate the objectives of the study.

4.2. Analysis Populations

The Safety population will include all subjects who receive any amount of the IP. The safety population will also be used for anti-AV-1 antibody assessment.

The PK population will include subjects who receive the full dose of AV-1 and have at minimum all samples from predose through 1.5 hours from the start of infusion to have sufficient concentration data to support accurate estimation of at least 1 PK parameter.

5. Subject Disposition, Protocol Deviations, and Follow-up

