10.4.1 Populations for Analysis

The analysis populations are as follows:

- The safety population will include all subjects who receive the full dose of the IP.
- The PK population will include subjects who receive the full dose of AV-1 and have at minimum all samples from predose through 1.5 hours from the start of infusion to have sufficient concentration data to support accurate estimation of at least 1 PK parameter.

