10.4.2 Statistical Analyses

Details of all statistical analyses will be described in a separate statistical analysis plan. All data collected will be presented in data listings. Data from subjects excluded from an analysis population will be presented in the data listings, but not included in the calculation of summary statistics.

For categorical variables, frequencies and percentages will be presented. Continuous variables will be summarized using descriptive statistics (number of subjects, mean, standard deviation [SD], minimum, median, and maximum).

All subjects receiving placebo across cohorts will be pooled into 1 treatment group for summary purposes.

Baseline demographic and background variables will be summarized overall for all subjects. The number of subjects who enroll in the study and the number and percentage of subjects who complete the study will be presented. Frequency and percentage of subjects who withdraw or discontinue from the study, and the reason for withdrawal or discontinuation, will also be summarized.

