- (l) Clinical laboratory testing will occur at Screening, Check-in, predose (within 60 minutes) and 48 hours after the start of the IP infusion on Day 1; and on Days 8, 15, 22, 43, 85, and 120. A complete list of assessments is provided in Section 7.2. Blood and urine samples will be collected under fasted conditions and prepared per the clinic's standard procedures.
- (m) Urine drug screen will occur at Screening and Check-in and on Days 22, 43, and 85 per the clinic's standard procedures and per Section 7.2.

- (n) Women of childbearing potential only. A serum pregnancy test will be performed at Screening and Check-in, and tests must be negative prior to enrollment and dosing, respectively.
- (o) After verification of eligibility, subjects will be randomly assigned before dosing on Day 1.
- (p) The start of the IP infusion will be called "0" hour and is denoted with grey shading. All doses of the IP will be administered intravenously over a period of 60 minutes. Subjects will maintain an upright (ie, seated or standing) position for at least 4 hours after the end of infusion.
- ^(q) Blood samples for PK analysis of AV-1 in serum will be collected predose (within 15 minutes); at 0.5, 1 (end of infusion), 1.25, 1.5, 2, 3, 4, 6, 8, 12, 24, and 48 hours after the start of infusion, Day 5 prior to discharge, and at the follow-up visits on Days 8, 15, 22, 29, 43, 57, 85, and 120 (or ET).
- A blood sample will be drawn on Day –1 and tested only if a suspected hypersensitivity reaction occurs during or following infusion on Day 1 at the discretion of the Investigator in consultation with the Sponsor. At the discretion of the Investigator, an additional blood sample will be drawn as soon as possible after the event occurs (Day 1) and again the following day (Day 2).
- (s) During fasting periods, subjects should have nothing to eat or drink except water from 10 hours prior to start of the IP infusion until 4 hours after the end of infusion.
- (t) During non-fasting periods when subjects are at the clinical site, subjects should receive standardized meals per the clinic's standard procedures that are scheduled at the same time in each treatment period during the study.

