8.2. Serum Concentrations

Blood samples for the determination of serum concentrations of AV-1 will be collected on Day 1 at the following time points: predose (within 15 minutes), and at 0.5, 1 (end of infusion), 1.25, 1.5, 2, 3, 4, 6, 8, 12, 24, and 48 hours after the start of the infusion and on Day 5 prior to discharge, and at the follow-up visits on Days 8 (+2), 15 (\pm 2), 22 (\pm 2), 29 (\pm 2),85 (\pm 5), and 120 (\pm 5) (or ET). AV-1 serum concentrations will be determined using a validated ECL ELISA method based on the MesoScale Discovery platform.

AV-1 serum concentration data will be summarized using descriptive statistics (N, n [non-missing values within the population], arithmetic mean, SD, CV%, median, minimum, and maximum) by dose group and scheduled sampling time. Individual and mean AV-1 serum concentration versus time data will be plotted by dose group. For ease of presentation, mean serum concentrations of AV-1 will be plotted by nominal time by dose group on both linear and semi-logarithmic scales.

Serum PK concentrations of AV-1 will be reported to the precision of the raw data in listing presentations; summary statistics for arithmetic mean, median, minimum, maximum, and SD will be reported to 3 significant figures; and CV% will be reported to 1 decimal place.

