8.4. Pharmacokinetic Statistical Analysis

Dose-proportionality for AV-1 will be evaluated for C_{max} , AUC_{0-tlast}, and AUC_{0- ∞}. A power model will be fitted to describe the relationship between Y (C_{max} , AUC_{0-tlast} and AUC_{0- ∞}) and X (dose) using the least-squares linear regression model [ln(Y) = ln(β_0) + β_1 ln(X)].

From each model, the intercept of regression line $[\ln(\beta_0)]$ and the slope of the regression line β_1 will be presented along with the 90% confidence interval (CI) of the slope. Dose-proportionality will be concluded if the 90% CI of the slope β_1 lies entirely within $[1+\ln(0.8)/\ln(r), 1+\ln(1.25)/\ln(r)]$, where r is a ratio that describes the dose range and is defined as the ratio of highest dose/lowest dose. If dose proportionality is not observed, then the lowest dose followed by the highest dose in succession will be removed, and the model will be fit again after the removal of a dose until dose proportionality is achieved or less than 3 dose groups remain.

The statistical analyses will be based on the PK population.

9. Anti-AV-1 Antibody Analysis

Blood samples for immunogenicity analysis will be collected at Check-in (Day -1) and on Days 29 (±2), 85 (±5), and 120 (±5) (or ET). A validated ECL ELISA method will be used for detection and confirmation of preexisting and treatment-emergent anti-AV-1 antibodies in serum samples based on the MesoScale Discovery platform that utilizes labeled AV-1 for detection of anti-AV-1 antibodies and treatment emergent antibodies.

Frequency and percentage of subjects who show detectable anti-AV-1 antibody signal in serum, including treatment-emergent anti-AV- antibodies, will be summarized for the safety population. Pharmacokinetic parameters may be displayed based on anti-AV-1 antibody status as applicable.

Anti-AV-1 antibody data will be presented in a data listing for the safety population.

10. Safety Analysis

All safety summaries and analyses will be conducted for the safety population.

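### One missed sample in the first 1.5 hours removes a subject from every PK summary and model, although these samples matter mainly for Cmax and Tmax

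*SAP*

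**What the plan says.** Both documents define the PK population by two conditions: the full dose of AV-1, and a complete early sampling window. In SAP 4.2 subjects must "have at minimum all samples from predose through 1.5 hours from the start of infusion to have sufficient concentration data"; protocol 10.4.1 likewise requires that they "have at minimum all samples from predose through 1.5 hours from the start of infusion". The stated purpose is "to support accurate estimation of at least 1 PK parameter". SAP 8.2 sets the serial samples "predose (within 15 minutes), and at 0.5, 1 (end of infusion), 1.25, 1.5, 2, 3, 4, 6, 8, 12, 24, and 48 hours", so the window holds five: predose, 0.5, 1, 1.25 and 1.5 h.

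The consequence of exclusion is in SAP section 4: "Data from subjects excluded from an analysis population will be presented in the data listings but not included in the calculation of summary statistics". Protocol 10.4.2 agrees. For dose proportionality, SAP 8.4 states: "The statistical analyses will be based on the PK population".

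Neither document gives a tolerance for one missed draw, a waiver, or a rule that admits a subject for some parameters and not others. Elsewhere the SAP does work at a finer level. SAP 8.1 leaves out missing concentrations one by one. SAP 8.3 computes parameters where the data allow, with at least three terminal points, an r² threshold of 0.80 and a limit on the extrapolated area.

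**The concern.** Entry to the PK population depends on 5 of the 22 samples in the protocol schedule (SAP 8.2 omits Days 43 and 57, leaving 20; that mismatch is a separate matter). AUC0-inf, CL, Vz and half-life are determined almost wholly by the later samples. A subject who misses only the 0.5 h draw can have a complete profile to Day 120 and still contribute nothing to the summaries of those parameters or to the AUC dose-proportionality models.

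PK is a secondary objective with six active subjects per dose, so each exclusion removes 1/6, or 17%, of a dose group. Protocol 5.2.2 provides for replacing subjects who withdraw and does not name a missed sample as a reason, so the loss need not be made good.

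**Working it through.** **Plan's own figure.** 5 cohorts × (6 + 2) = 40 subjects, of whom 5 × 6 = 30 receive AV-1. This matches SAP 4.1. The documents state no expected number of PK exclusions, no PK values, no miss rate and no CV. Everything below that needs them is an assumption.

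**1. Effect of one missing early sample.** Assumed: noise-free two-compartment profiles, 60-minute infusion, CL 0.1 to 1.0 L/day, V1 2.5 to 3 L, V2 3 L, Q 0.5 to 24 L/day. These give distribution half-lives of 0.9 to 47 h and terminal half-lives of 7 to 44 days. AUC is by linear trapezoid and AUC0-inf = AUC0-tlast + Ct/λz, as in SAP 8.3, with λz from the last three points. Both sampling schedules were run.

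| Omitted | AUC0-tlast, AUC0-inf, CL | AUC0-48 | Half-life | Cmax |
|---|---|---|---|---|
| Any one of 0.5, 1, 1.25, 1.5 h | at most 0.083% | at most 0.31% | 0 | changes only if 1 h is lost: −0.2% to −7.8% |
| All four | at most 0.67% | at most 2.5% | 0 | −0.8% to −24% |

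Vz is Dose/(AUC0-inf × λz). With λz unchanged, it moves only as AUC0-inf does.

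Hand check of the worst single omission (1 h), taking a linear rise to Cmax at 1 h and a flat level to 1.25 h:
- Area from 0.5 to 1.25 h with the sample: 0.75 × 0.5 + 1 × 0.25 = 0.625 Cmax·h. Without it: 0.75 × 0.75 = 0.5625. Loss: 0.0625 Cmax·h.
- With Cmax ≈ Dose/3 L, the loss is 0.0208 Dose·h/L.
- At CL 0.2 L/day, AUC0-inf = Dose × 24/0.2 = 120 Dose·h/L, so the loss is 0.017%.
- At CL 1.0 L/day, AUC0-inf = 24 Dose·h/L, so the loss is 0.087%, against 0.083% in the full calculation.

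A missing predose sample was not simulated. Zero is the natural value for a first dose of a new antibody, but the SAP does not state it.

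**2. Subjects excluded.** For an assumed independent miss rate m per sample, the exclusion chance is p = 1 − (1 − m)^5. The expected number is 30p, and the chance of at least one exclusion in a group of six is 1 − (1 − p)^6.

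| m | p | Expected of 30 | At least 1 of 6 |
|---|---|---|---|
| 0.5% | 2.5% | 0.7 | 14% |
| 1% | 4.9% | 1.5 | 26% |
| 2% | 9.6% | 2.9 | 45% |

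If a subject's misses always came together, p would be m itself, giving 30m = 0.15, 0.3 or 0.6 subjects.

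**3. Effect on the dose-proportionality interval.** The SAP 8.4 margin with r = 1000/30 is ln(1.25)/ln(33.3) = 0.2231/3.5066 = 0.0636 either side of 1. The half-width of the 90% CI for the slope is t(0.95, n−2) × √ln(1+CV²)/√Sxx, where Sxx is the sum of squares of ln(dose).
- All 30 subjects: Sxx = 46.29, t = 1.701.
- One 30 mg subject lost: n = 29, Sxx = 42.53, t = 1.703.

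| Assumed CV | All 30 | One 30 mg subject lost |
|---|---|---|
| 20% | 0.050 | 0.052 |
| 25% | 0.0616 | 0.0643 |
| 30% | 0.073 | 0.077 |

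Worked at 25%: √ln(1.0625) = 0.2462; 1.701 × 0.2462/6.804 = 0.0616; 1.703 × 0.2462/6.522 = 0.0643. At 20% the half-width is inside the margin either way, and at 30% it is outside either way. Only near 25% does one lost 30 mg subject decide whether the margin can be met on the full dose range.

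**The case against.** The case for leaving the rule alone has real substance.

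- **The window serves Cmax and Tmax.** Cmax is a secondary endpoint and one of three dose-proportionality parameters. Losing the 1 h sample biases it by 0.2% to 7.8% in the assumed profiles. A reader might infer that the requirement buys no accuracy at all; for Cmax that is wrong. This stands, and a Cmax/Tmax condition should remain.
- **Terminal parameters are already gated.** A reader might infer that the rule is also too lax, because a subject with five early samples and nothing later gets in. The documents do not support that: such a subject can yield Cmax and Tmax, which meets the stated aim of one parameter, and SAP 8.3 and protocol 10.4.3 keep them out of the terminal parameters. This stands.
- **Misses should be rare.** Subjects are confined, the infusion is observed, protocol section 6 gives PK draws precedence over other sampling, and actual times are used, so a late draw is not a missing one. Misses may also cluster, as with a failed line. This stands as a limit on size. A 5% rate would give 22.6% excluded, or 6.8 of 30, but nothing in the documents makes that rate plausible.
- **The rule is objective and identical in both documents.** True, but a parameter-level rule fixed in advance is equally objective.

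What the objection does not answer is why a missed 0.5 h draw should remove a sound half-life or clearance estimate.

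**Conclusion.** The point holds in a limited form. Read literally, one missing sample out of five excludes a subject from every PK summary and from the dose-proportionality models. A reader might take this to mean that the profile is lost; it is not, since it remains in the listings.

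For AUC0-tlast, AUC0-inf, CL, Vz and half-life the exclusion has almost no accuracy benefit: under 0.1% for any one post-dose sample across the assumed kinetics. For Cmax and Tmax the end-of-infusion sample is needed. Expected losses are about 0.7 to 2.9 of 30 at assumed independent miss rates of 0.5% to 2%, and fewer with clustering. The effect on the slope interval is small and decisive only in a narrow range of CV. No power calculation or formal efficacy conclusion depends on it. All PK values, miss rates and CVs are assumptions. This is a minor improvement, worth making because it costs little.

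**What to change.** In SAP 4.2 and protocol 10.4.1, keep the full-dose-of-AV-1 condition and replace the five-sample condition with at least one evaluable PK parameter. Then state evaluability by parameter in SAP 8.3:

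- Cmax and Tmax require the end-of-infusion sample.
- AUC0-inf, CL, Vz and half-life follow the existing λz, r² and extrapolation rules.
- AUC0-tlast and AUC0-48 are computed where data allow, with missing concentrations left out as SAP 8.1 already provides. Add a sentence saying what time-zero value is used if the predose sample is missing.

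The full-dose condition should not be loosened in the process. Otherwise partly infused subjects would enter CL and the power model with no rule for them.

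The cost is one definition in two places and a few lines in SAP 8.3, settled before unblinding. The number of subjects may differ by parameter, which the r² and extrapolation rules already allow; each table should show n for each parameter.

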5.1. Disposition

Subject disposition will be summarized by treatment and total for all randomized subjects.

The number of subjects who are randomized in the study and the number and percentage of subjects who complete the study will be presented. Frequency and percentage of subjects who withdraw or discontinue from the study, and the reason for withdrawal or discontinuation, will also be summarized.

Subject disposition data, analysis populations, and randomization data will be presented in data listings.

5.2. Protocol Deviations

A protocol deviation is any change, divergence, or departure from the study design or procedures defined in the protocol. An important deviation (sometimes referred to as a major or significant deviation) is a subset of protocol deviations that leads to a subject being discontinued from the study, or significantly affects the subject's rights, safety, or well-being or the completeness, accuracy, and reliability of the study data. An important deviation can include nonadherence to inclusion or exclusion criteria or nonadherence to Food and Drug Administration regulations or International Council for Harmonisation (ICH) E6(R2) guidelines.

Protocol deviations will be documented by the clinical monitor throughout the course of monitoring visits. The Investigator will be notified in writing by the monitor of deviations. The Institutional Review Board should be notified of all protocol deviations, if appropriate, in a timely manner.

Important protocol deviations will be summarized for all randomized subjects.

All protocol deviations will be presented in a data listing, including the categorization of the deviation as important or not. Details of admission criteria deviations will be presented in a separate data listing.

6. Demographics and Baseline Characteristics

6.1. Demographics

Demographic and baseline characteristics will be summarized by treatment and total for Safety population.

The demographic characteristics consist of age (years), sex, race, and ethnicity. The baseline characteristics consist of baseline weight (kg), height (cm), and body mass index (kg/m²). Percentages will be based on the total number of subjects in the Safety population.

Subject demographic and baseline characteristics will be presented in a data listing.

6.1.1. Medical History

Medical history will be coded using the Medical Dictionary for Regulatory Activities (MedDRA, version to be delineated in the Clinical Study Report [CSR]).

Medical history will be presented in a data listing for safety population.

7. Treatments, Medications, and Meals

7.1. Prior and Concomitant Medications

Information regarding prior medications taken by the subject within the 30 days before signing the informed consent form will be recorded in the subject's electronic case report form (eCRF).

Any concomitant medication deemed necessary for the welfare of the subject during the study may be given at the discretion of the investigator. If a concomitant medication is taken, except for those specified in the protocol, a joint decision will be made by the investigator and the Sponsor to continue or discontinue the subject based on the time the medication was administered, its pharmacology and PK, and whether the use of the medication will compromise the safety of the subject or the interpretation of the data. The investigator is responsible for ensuring that details regarding the medication are adequately recorded in the eCRF.

Prior and concomitant medications and therapies will be coded using the latest version of the World Health Organization Drug Dictionary.

All prior and concomitant medications will be presented in a data listing for the safety population.

7.2. Medical and Surgical Treatment Procedures

All medical and surgical treatment procedures will be coded using MedDRA (version to be delineated in the CSR). All medical and surgical treatment procedures will be presented in a data listing for safety population.

7.3. Study Drug Administration

All doses of study drug will be administered at the study site under direct observation of site personnel and recorded in the eCRF. Study site personnel will confirm that the subject has received the dose of study drug. The start and stop date/time, and amount of study drug dosing will be recorded on the appropriate page of the eCRF. If a subject does not receive study drug, the reason for the missed dose will be recorded.

All study drug administration data will be presented in a data listing.

8. Pharmacokinetic Analysis

8.1. Data Handling

Serum concentrations that are below the limit of quantification (BLQ) will be treated as zero for calculation of descriptive statistics. Mean BLQ concentrations will be presented as BLQ, and the SD and CV will be reported as not applicable.

For PK analysis, BLQ values will be treated as zero with the exception that a BLQ value between 2 quantifiable concentrations will be set as missing. If consecutive BLQ concentrations are followed by quantifiable concentrations in the terminal phase, those concentrations after BLQ concentrations will be treated as missing.

Missing concentrations will be excluded from all calculations and PK analyses.

